**Methods:** This research project will be conducted with Cleveland Clinic IRB approval and waived patients consent. (see Human Subjects section for justification). The trial will be registered at ClinicalTrials.gov (NCT04701762, date of registration January 8 2021) before enrolling any patients. A full statistical analysis plan will be developed before any data are evaluated. Reporting will be consistent with the CONSORT guidelines for pilot trials.

**Design:** The proposed quality improvement project will be conducted in an isolated set of 22 operating rooms (J operating suites) at the Cleveland Clinic Main Campus which is largely staffed by a consistent team of anesthesia attendings, nurse anesthetists and anesthesia residents and fellows with variable level of experience. Most operations in this suite are cardiac, thoracic, or vascular surgeries. Nearly all require general anesthesia, and most patients are hospitalized at least overnight.

We plan a cluster randomized multiple crossover quality improvement project. The J operating suites will be divided into 2 separate clusters consisting of 11 operating suites each (cluster 1: operating suites 60 to 70, and cluster 2: operating suites 71 to 81). Clusters were formed by physical proximity to make it as logistically feasible as possible to conduct the trial.

Randomization will consist of randomizing cluster 1 to use either videolaryngoscope or direct laryngoscope, and cluster 2 to the alternative device in one-week blocks.

Randomization, 1:1 and unstratified, will be based on computer-generated codes maintained in a web-based system that investigators will access one day before each new treatment block begins. Randomization allocations will be verbally communicated to anesthesia personnel directly and by signs prominently displayed on each anesthesia machine. In previous similar trials, compliance with designated allocations exceeded 97%.

Design notes: Cluster randomized multiple crossover cluster trials are analogous to individual patient crossover trials, except that each cluster is crossed over to the other treatment in the next period instead of individual patients crossing over. They differ from cluster randomized trials (CRT) in that each cluster receives each treatment multiple times instead of each cluster only receiving one of the interventions during the trial.

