**Subject selection:** We propose to enroll adults scheduled for elective or emergent cardiac, thoracic, or vascular surgery in the designated operating room suite who require endotracheal intubation for general anesthesia. We will enroll male and female patients of any race and ethnicity. Using the videolaryngoscope as the first line airway device is likely to be beneficial and unlikely to augment risk.

Inclusion criteria:

1. Elective or emergent surgery requiring oral endotracheal intubation for general anesthesia.

Exclusion criteria:

1. The attending anesthesiologist prefers a specific approach for a particular patient;
2. Awake fiberoptic intubation is clinically indicated;
3. Insertion of double-lumen tube.

**Protocol:** There will be no restrictions on anesthesia management, and anesthesia providers will be free to use any type of general anesthesia, supplemented by any type of regional anesthesia including neuraxial and peripheral nerve blocks. Fluid management, type and dosage of anesthesia medications, and postoperative analgesia will also be per clinical preference.

Our clinical routine is to intubate patient's supine on the OR table. Patients will be pre-medicated with midazolam 0-2 mg IV, as clinically appropriate. Patients will be pre-oxygenated until the fraction of expired oxygen exceeds 80%. General anesthesia will be induced as preferred by the attending anesthesiologist, usually with a combination of lidocaine 1 mg/kg, propofol 1-3 mg/kg or etomidate 0.2-0.3 mg/kg, fentanyl 1-3 µg/kg, and

succinylcholine 1.5 mg/kg or rocuronium 1.0 mg/kg. Our routine practice is to perform endotracheal intubation after confirming adequate muscle relaxation. In qualifying patients, initial laryngoscopy will be performed using one of the following methods:

1. Direct laryngoscopy with an appropriately sized Macintosh or Miller blade (usually size 3 or 4);
2. Indirect laryngoscopy using a GlideScope videolaryngoscope with an appropriately sized blade (usually size 3 or 4). The GlideScope (Verathon, Bothell, WA 98011) is an FDA-cleared commercially available portable videolaryngoscope.

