#### **Limitations and anticipated difficulties:**

The proposed study will be by far the largest randomized trial of airway management. It will include patients with a broad range of airway characteristics, only excluding patients with airway pathologies so severe that responsible clinicians prefer an initial fiberoptic intubation. Our finding should therefore be broadly generalizable to adult surgical patients.

This project will be performed in the J operating rooms area of the Cleveland Clinic Main Campus. This area includes 22 operating rooms, which is largely staffed by a consistent team of anesthesia attendings and nurse anesthetists. We have substantial experience with large studies in this surgical area, and have had consistently excellent collaboration with the entire anesthesia team, along with the surgeons.

We selected the GlideScope videolaryngoscope because it is currently used routinely at the Cleveland Clinic and all anesthesia personnel are familiar with the device. Finally, GlideScope videolaryngoscopy devices and blades have been donated by the manufacturer so there will be no cost to patients or the institution.

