### **Statistical Analysis:**

We will assess the balance of randomized groups (videolaryngoscopy vs. direct laryngoscopy) on baseline and demographic characteristics using the absolute standardized difference (ASD), defined as the absolute difference in means, mean ranks, or proportions divided by the pooled standard deviation. Any characteristics with  $ASD > \text{maximum of } 0.10 \text{ and } 1.96\sqrt{(n_1 + n_2)x(n_1n_2)}$  will be considered imbalanced and will be adjusted for in the primary and secondary analyses.

All primary and secondary analyses will use the modified intent-to-treat principle, including all randomized patients who received any of the study. We will conservatively assign all missing outcome values as the highest possible score in the control group (direct laryngoscopy) and the lowest possible score in the treatment group (GlideScope videolaryngoscopy) for all primary and secondary analyses. Assumptions of statistical tests will be assessed using graphical and statistical methods.

For the primary outcome, number of intubation attempts will be calculated as the number of attempts with either device, independent of whether or not a patient was crossed over to the other device due to failure with the randomized device. The ordinal categories will be 1, 2, 3, and  $> 3$  attempts. We will assess the effect of videolaryngoscopy vs. direct laryngoscopy on the number of intubation attempts using a generalized linear mixed effects cumulative logit model in which we consider the outcome to be ordinal and consider the operating room within cluster as a random effect. In sensitivity analyses we will assess the treatment effect using a Wilcoxon-Mann-Whitney test and a proportional odds logistic regression model, if the assumption of proportional odds holds. In all analyses, we will adjust for variables imbalanced at baseline.

For the secondary (binary) outcomes of 1) intubation failure and 2) collapsed composite of any airway or dental injury we will assess the effect of videolaryngoscopy vs. direct laryngoscopy using a generalized linear mixed effects model in which we consider the outcome to be binary and consider the operating room within cluster as a random effect.

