**Interim Analyses.** We will conduct interim analyses for efficacy and futility at each 25% of the planned enrollment using a group sequential design with a gamma spending function, with gamma parameter of -4 for efficacy and -1 for futility. Assuming the alternative hypothesis is as specified below in Sample Size Considerations, there will be a cumulative 9.4% probability of crossing a stopping boundary at the first look, 40% through the 2nd look, 78 % through the 3rd look and 100% by the last. Stopping boundaries will *not* be binding – the decision to stop or continue the trial will be made by the DSMB which will consider all available information in their decision.

**Sample size considerations.** Sample size is based on the primary outcome, the number of intubation attempts (with either device). About 5,000 operations per year will be performed during the anticipated 3-year enrollment period. Based on a previous study, we expect that about 10% of patients may require more than 1 intubation attempt in the direct laryngoscopy group versus about 4% in the videolaryngoscopy group. (Direct laryngoscopy 1 attempt: 90%, 2 attempts: 4%; Videolaryngoscopy 1 attempt: 96%, 2 attempts: 4%). However, we plan the study to detect a slightly smaller effect, which also would be clinically relevant.

We assume for sample size calculation that the proportion having 1, 2, 3 or more than 3 attempts will be 0.90, 0.04, 0.03, 0.03 in the direct laryngoscopy group and 0.92, 0.04, 0.02, 0.02 with videolaryngoscopy. To detect this difference or a larger one with 90% power at the 0.05 significance level with a Mann-Whitney test we would need a total of 8,800 patients, before accounting for interim analyses or within-cluster correlations. Accounting for a small within-cluster correlation of 0.01 and even smaller within-cluster

between-period correlation of 0.009, the required total sample size  is 13,112. Further adjustment for interim analyses requires a maximum total of 14,943 patients.

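### The mixed models leave out the cluster-by-week variation that the sample size assumes; for the primary outcome, type I error is between 5.0% and about 5.5% (minor)

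*Combined protocol and SAP*

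**What the plan says.** Design (under Methods) sets the unit of assignment: "Randomization will consist of randomizing cluster 1 to use either videolaryngoscope or direct laryngoscope, and cluster 2 to the alternative device in one-week blocks". Each cluster has 11 rooms.

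Statistical Analysis fits a cumulative logit mixed model to the number of attempts and binary mixed models to intubation failure and injury. Each is to "consider the operating room within cluster as a random effect". The exploratory blood pressure and heart rate models follow the same pattern. The sensitivity analyses for the primary outcome, a Wilcoxon-Mann-Whitney test and a proportional odds model, are stated without any clustering term.

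Sample size considerations says "we would need a total of 8,800 patients, before accounting for interim analyses or within-cluster correlations". It continues "Accounting for a small within-cluster correlation of 0.01 and even smaller within-cluster" "between-period correlation of 0.009, the required total sample size" and arrives at 13,112, then 14,943 after the interim looks. Accrual is given as "About 5,000 operations per year will be performed during the anticipated 3-year enrollment period".

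The Internal Pilot Study paragraph re-estimates both correlations at the first interim analysis, but only to resize the trial. The early-versus-late analysis by trial month is a treatment interaction with graphs, not a variance component. No section adds a cluster-week term, a robust variance or a design-based test.

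**The concern.** If patients in the same cluster and week are more alike than patients in the same cluster in different weeks, the extra likeness sits at the level at which the device is assigned. A time-constant room effect removes stable differences between rooms, and with them between clusters. It leaves cluster-week variation in the residual, where it is treated as independent patient noise. Standard errors are then too small and the test rejects too often.

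The plan cannot regard this component as absent, because it sets the within-period correlation above the between-period one. Every mixed model in the plan has the same gap, and the listed sensitivity analyses would not reveal it. The same model would presumably also feed the interim looks.

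**Working it through.** **Inputs.** From the documents: correlations 0.01 (ρ) and 0.009 (η); 5,000 operations a year for 3 years; maximum 14,943 patients; two clusters of 11 rooms; one-week blocks; alpha 0.05; four looks with gamma -4 for efficacy. Assumed: a two-sided test, since sidedness is not stated. Derived: m = 5,000/52/2 ≈ 48 patients per cluster-week (14,943/156/2 = 47.9 agrees), and 48/11 ≈ 4.4 per room-week. Not in the documents: s, the share of week variation common to both clusters.

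**The plan's own figures.**
- 8,800: a two-sided comparison of 10% with 8% at 90% power, with continuity correction, gives 8,802.
- 13,112: 13,112/8,800 = 1.49. The cluster-crossover design effect is 1 + (m - 1)ρ - mη = 0.99 + 0.001m. It equals 1.49 at m = 500. At m = 48 it is 1.038, and 8,800 × 1.038 ≈ 9,134.
- 14,943: non-binding gamma spending (-4 and -1) inflates by 1.135, giving 14,879, within 0.5%.

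The stated 13,112 therefore fits about 500 patients per cluster-period. At one-week blocks that would be 500 × 2 × 52 = 52,000 operations a year against the stated 5,000. This mismatch needs its own reconciliation and is not used below.

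**Size of the error.** Scale the total variance to 1: 0.009 stable, 0.001 cluster-week, 0.99 residual. The room-only model uses 0.99 + 0.001 = 0.991 per patient. The device contrast truly has 0.99 + 0.001m(1 - s), because the clusters use opposite devices in the same week and shared week effects cancel. So

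ratio = [1 - ρ + m(ρ - η)(1 - s)]/(1 - η), and type I error = 2[1 - Φ(1.96/√ratio)].

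| Case | Ratio | Type I error | Simulated |
|---|---|---|---|
| m = 48, none shared | 1.038/0.991 = 1.047 | 5.55% | 5.6% |
| m = 48, half shared (assumed) | 1.014/0.991 = 1.023 | 5.27% | 5.2% |
| m = 48, all shared | 0.990/0.991 = 0.999 | 5.0% | 5.1% |
| m = 30 (assumed), none shared | 1.020/0.991 = 1.029 | 5.34% | 5.3% |
| Excess at room-week level, m = 4.4 | 0.9944/0.991 = 1.003 | 5.04% | 5.2% |

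In the first row the standard error is understated by 2.3% (√1.047 = 1.023). The m = 30 row allows for exclusions such as "Insertion of double-lumen tube". The first four rows were simulated with 40,000 null trials each (Monte Carlo error about 0.11 points): 156 weeks, 22 rooms, Poisson counts, the plan's 0.90/0.04/0.03/0.03 distribution, and a linear midrank-score approximation to the cumulative logit model. The last row used 20,000 trials with normal outcomes (Monte Carlo error about 0.15 points).

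**Four looks.** With gamma -4 spending, 0.025 per side and boundaries 3.16, 2.82, 2.44 and 2.01, a ratio of 1.047 gives 5.6% overall instead of 5.0%. Stopping remains a non-binding decision of the monitoring board.

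**Dependence on the gap.** The error grows with ρ - η. If the gap were twice as large (η = 0.008, assumed), the ratio with m = 48 and nothing shared would be (0.99 + 0.096)/0.992 = 1.095, and the error about 6.1%.

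**The case against.** **It is too small to matter.** At worst the standard error is 2.3% too small, and no conclusion of the trial plausibly turns on that. This stands as a limit on severity. It does not make the model right, since the plan itself assumes the missing component.

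**The upper figure rests on inputs that the plan does not give.** This stands. The weekly size is derived and the shared fraction is unknown. The suite, "which is largely staffed by a consistent team of anesthesia attendings and nurse anesthetists", may well have week effects common to both clusters. The excess could also sit at room-week level, where the error is about 5.04%. The result is therefore a range that starts at 5.0%.

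**The remedy has its own faults.** In simulation the cluster-week variance is estimated at zero in about 29% of full-size trials and about 42% at the first look, and the model then reverts to the present one. If week effects are partly or fully shared, the model test is slightly conservative (4.6% and 4.4%). This stands, and it is why the fix also requires a week-paired analysis, which held 5.0% to 5.1% in every simulated case.

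**A full statistical analysis plan is promised before data are evaluated.** That is a suitable place for the repair, but the model as now written still omits the term.

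**Stronger readings.** A reader might take 1.49 as the variance inflation that the analysis ignores, which would put type I error at about 11%, or about 12% over the four looks. The documents do not support this: 500 patients per cluster-week cannot occur at the stated accrual. For the same reason, the rise to 13,112 is not evidence that N covers weekly variation.

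**Conclusion.** The concern holds and is minor. Assignment is by cluster and week, the planning correlations imply a cluster-period component, and none of the mixed models contains it. For the primary outcome, intervals are at most slightly too narrow: type I error is 5.0% to about 5.5% for a single test, and up to about 5.6% over the four looks.

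This rests on correlations of 0.01 and 0.009, about 48 patients per cluster-week, a two-sided test, and a normal approximation with equal cluster-week sizes. The omission itself is certain from the text. Its size is only as good as the planning correlations, and a gap above 0.001 would raise it.

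A reader might infer a serious error in the failure, injury or haemodynamic analyses. The plan gives no correlations for those outcomes, so the omission there is structural and cannot be sized.

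**What to change.** 1. Add a cluster-by-week random effect to the primary, secondary and exploratory mixed models, keeping the room effect.
2. Use the same model at any interim look still to come. The documents do not say whether one has occurred. At 96 patients a week, a quarter of 14,943 (3,736) takes about 39 weeks from first enrollment on 29 March 2021, so late December 2021, before version 7. At 60 a week (assumed) it takes about 62 weeks, so about June 2022. If a look has occurred, document the change and its timing.
3. Pre-specify a week-paired comparison of the two clusters as the required sensitivity analysis, reported beside the model result, especially when the cluster-week variance is estimated at zero.
4. Use a permutation test only if each week was independently randomised. Design describes codes consulted before each block, but its design notes can be read as strict alternation. Under alternation only two allocation sequences exist and the test cannot reach p < 0.05. The two descriptions must be reconciled first.
5. Separately, reconcile the 1.49 inflation with one-week blocks.

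The cost is wording, one variance component and one sensitivity analysis. Intervals become about 2% to 3% wider, and the model test is slightly conservative if weeks are shared. Simulated power at 14,943 patients under the plan's alternative (final test only, nothing shared) is 99.2% with the present model, 99.1% with the added term and 99.0% for the week-paired test.

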**Measurements:** All data will be obtained from electronic anesthesia and hospital records. No tests or evaluations will be done specifically for this trial. Preoperative airway characteristics and difficulties encountered during anesthetic induction will be recorded per routine (*table 1*). Demographic and morphometric characteristics will be obtained from the electronic records including age, sex, race, and body mass index. Type of surgery will be characterized from ICD-10 codes using AHRQ Clinical Classifications Software. All routine anesthetic variables, including medications, will be recorded by routine by our electronic anesthesia record keeping system. We will also capture the level of training of the person making the first intubation attempt and the final intubation attempts (if a switch of anesthesia providers occurred).

Table 1:

Preoperative airway characteristics	Neck- full range of motion
	Limited neck extension
	Limited neck flexion
	Limited neck extension and flexion
	Short neck
	Short thyromental distance
	Small mouth opening
	Non-compliant submandibular space
	Beard presents
Difficulties encountered during anesthesia induction	Anterior larynx
	Expected difficulties
	Large epiglottis
	Large tongue
	MAC safe cannula
	Poor jaw range of motion
	Poor neck range of motion

	Recessed chin
	Sniffing position
	Stylette required
	Unexpected difficulties

Per our clinical routine, an initial attempt will be defined by insertion of a laryngoscope blade and/or endotracheal tube into a patient's mouth. Subsequent attempts will be defined by re-insertion of an endotracheal tube, or insertion of the same or a new laryngoscope blade. Attempts will be recorded per routine by anesthesia providers in the electronic record.

*Intubation failure* will be defined by the responsible clinician switching to an alternative laryngoscopy device for any reason at any time, or by more than 3 intubation attempts.

*Airway injury* will be defined as any bleeding or apparent injury to the lips, mouth, pharynx, vocal cords, or other airway structures recorded by the anesthesia team.

*Dental injury* will be defined as any apparent injury to the teeth as recorded by the anesthesia team.

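### Covariates enter the outcome models only through an observed-imbalance trigger that ordinary covariates will almost never trip by the final analysis, so that analysis is in effect unadjusted and a modest amount of power is forgone

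*Combined protocol and SAP*

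**What the plan says.** Under Statistical Analysis, baseline balance is judged by the ASD. A characteristic above the larger of 0.10 and a term in 1.96 and the two group sizes "will be considered imbalanced and will be adjusted for in the primary and secondary analyses". The primary-outcome paragraph repeats the rule after the sensitivity analyses: "In all analyses, we will adjust for variables imbalanced at baseline". The only other term described for the primary and secondary models, besides treatment, is a random effect for operating room nested in cluster. The exploratory haemodynamic outcomes follow the same imbalance rule.

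Candidate predictors are available. Under Measurements, "Demographic and morphometric characteristics will be obtained from the electronic records including age, sex, race, and body mass index", and Table 1 has a block of preoperative airway items. The paragraph on treatment effect heterogeneity names 20 factors, many of them airway features, but only for exploratory interaction tests.

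Interim Analyses sets a look at each quarter of enrolment. It does not say whether covariates are fixed, selected again or left out at each look.

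**The concern.** Selection rests on observed imbalance and not on prognostic value. In a trial this large, chance imbalance on an ordinary characteristic is far below 0.10, so a predictor of difficult intubation would stay out of the model however strongly it relates to the outcome. Two things are at stake. One is power that data already in the record could supply. The other is prespecification: if a covariate were flagged at an early look and not later, the odds ratio being monitored would change meaning between looks.

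**Working it through.** **The plan's sample size, which sets the group sizes.** The chain is 8,800, then 13,112, then 14,943.
- The planned distributions are "0.90, 0.04, 0.03, 0.03 in the direct laryngoscopy group and 0.92, 0.04, 0.02, 0.02 with videolaryngoscopy", so more than one attempt occurs in 10% versus 8%. A continuity-corrected two-proportion test (two-sided 0.05, 90% power) gives 8,802 in total. The named Mann-Whitney test with ties gives 7,977.
- 13,112 / 8,800 = 1.49. This equals 1 + (m - 1)(0.01) - m(0.009) at m = 500 per cluster-period. One-week blocks at 5,000 operations a year give 5,000 / 52 / 2, about 48 per cluster-week, and a design effect of 1.04.
- Four looks with the stated gamma spending inflate 13,112 by about 1.129, to 14,800, within 1% of 14,943.

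**How often the trigger fires by chance.** Take equal arms and read the second threshold term as 1.96 × sqrt((n1 + n2)/(n1 × n2)). With total N, SE(ASD) = sqrt(4/N). With design effect DE, P(fire) = 2 × [1 - Phi(0.10 / (SE × sqrt(DE)))]. For any of 20 independent covariates it is 1 - (1 - P)^20.

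| Look | N | 1.96 term | 0.10 / SE | One covariate, DE 1 | Any of 20, DE 1 | Any of 20, DE 1.49 |
|---|---|---|---|---|---|---|
| 1 | 3,736 | 0.064 | 3.06 | 0.22% | 4.4% | 22% |
| 2 | 7,472 | 0.045 | 4.32 | 0.0015% | 0.03% | 0.8% |
| 3 | 11,207 | 0.037 | 5.29 | 1.2e-7 | 2.4e-6 | 0.03% |
| 4 | 14,943 | 0.032 | 6.11 | 1e-9 | 2e-8 | 0.001% |

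The 1.96 term exceeds 0.10 only below 4 × (1.96/0.10)^2, about 1,537 patients, so the floor governs at every look. At DE 1.04 the first-look figure for any of 20 is 5.3%. Applying the outcome's design effect to covariates is an assumption.

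**Covariates linked to the room clusters.** In a two-cluster weekly simulation with assumed prevalences:
- 15% versus 25% in the two clusters fires 4% to 8% of the time at look 1 and in 0 of 2,000 runs at the end if allocation is re-randomized weekly. Under strict alternation it is about 1% and 0.
- 30% versus 70% fires about 45% of the time at look 1 and 13% to 14% at the end under weekly re-randomization. Under alternation it is at most 1.6% and 0.

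The Design section speaks both of randomizing in weekly blocks and of crossing each cluster over in the next period, so either case may apply.

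**Bias from leaving a covariate out.** The typical final chance ASD is about 0.016. For a predictor with assumed prevalence 10% and risk ratio 2, the prevalence difference is 0.016 × sqrt(0.1 × 0.9) = 0.0048. Risk without the predictor is 0.10/1.1 = 0.091. The shift is 0.0048 × 0.091 = 0.0004, or 0.04 points. Across prevalence 5% to 20% and risk ratio 2 to 3 it is 0.03 to 0.09 points, against a planned effect of 2 points.

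**What adjustment would gain.** Assume a normal prognostic score on the logit scale, independent patients, and a binary outcome (more than one attempt) at marginal rates 10% and 8%. The unadjusted odds ratio is (0.08/0.92)/(0.10/0.90) = 0.783. Efficiency = (ratio of log odds ratios)^2 / (ratio of SEs)^2, adjusted over unadjusted. Power = Phi(3.242 × sqrt(efficiency) - 1.960), where 3.242 = 1.960 + 1.282 gives 90% without adjustment.

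| Score SD | AUC | Adjusted OR | Change in SE of log OR | Efficiency | Power |
|---|---|---|---|---|---|
| 0.3 | 0.58 | 0.781 | +0.4% | 1.008 | 90.2% |
| 0.6 | 0.66 | 0.777 | +1.6% | 1.032 | 90.9% |
| 0.9 | 0.73 | 0.768 | +3.7% | 1.075 | 91.9% |
| 1.2 | 0.79 | 0.756 | +6.7% | 1.138 | 93.3% |

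**The case against.** The strongest defence is that validity is not at risk. An imbalance rule stated in advance, with an unadjusted model as default, leaves a randomized comparison unbiased, and the shift from a typical chance imbalance is tiny. That stands. So does the point that predictor strength is unknown: no AUC or R-squared is given, the exclusions for attending preference and awake fiberoptic intubation may weaken prediction, and the title of a large-centre study in the reference list reports no association of degree of obesity with more than one attempt. The weak end of the range therefore has to be shown.

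Four stronger readings are tempting, and the documents do not support them:
- **Nothing could ever be flagged.** A reader might take the sign inside the square root as a product, which would make the threshold enormous. The formula was read from PDF by a program, and the ratio is the usual form. No criticism should rest on that character.
- **The rule does no useful work.** It can fire at look 1, it can catch a strongly cluster-linked characteristic later, and it could reveal non-chance imbalance, for instance if the attending-preference exclusion were used after allocation was known.
- **The model is re-selected at all four looks.** Interim Analyses is silent, so this is an open question and not a stated procedure. A rule that seldom fires also seldom changes the model; a change is realistic mainly between look 1 and later looks. Boundaries are non-binding.
- **Precision is given away.** The standard error of the log odds ratio rises on adjustment. Power improves because the conditional odds ratio lies further from 1; the interval does not narrow.

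Nor are the airway items wholly unused, since the heterogeneity analyses draw on them.

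**Conclusion.** The point holds as one of efficiency and prespecification. For ordinary covariates the trigger is negligible from the second look on: at most 0.8% for any of 20 at look 2 and about 0.001% at the end, even at design effect 1.49. The final primary and secondary models will therefore in practice carry no baseline covariates. The exceptions are the first look (about 4% to 22% for any of 20) and characteristics strongly tied to room cluster. The plan should say what happens to the covariate set across looks.

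The cost is about 0.8% to 14% in efficiency, or 0.2 to 3.3 points of power from a base of 90%. This rests on the assumed SD of 0.3 to 1.2, a binary outcome and no clustering. It is worth changing because the data are already recorded, but it does not undermine the trial's conclusion.

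Two details need correcting in any case. A plain Wilcoxon-Mann-Whitney test cannot take covariates, so adjustment in every analysis cannot be carried out as written. Also, several factors that the heterogeneity paragraph treats as baseline (anterior larynx, large epiglottis, stylette required) appear in Table 1 among the items noted at induction.

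**What to change.** Replace the trigger with one short list of preoperative covariates, fixed now and used unchanged at every look. Age, sex, BMI, emergency versus elective surgery and a non-overlapping coding of the preoperative block of Table 1 would serve; the neck-movement items overlap as listed. Use it in the primary cumulative logit model and, as event counts allow, in the secondary models. Add a simple rule for missing covariate values, since all data come from routine records and the trial timeline shows a change of record system. Do not adjust for Table 1 items recorded during induction, because the device may affect them. Report ASD descriptively, put any adjustment for a flagged imbalance in a sensitivity analysis, and leave the Wilcoxon-Mann-Whitney analysis unadjusted.

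No new data are needed. The odds ratio becomes conditional on the listed covariates, its log-scale standard error rises by about 0.4% to 7%, and the mixed model is somewhat larger, with a risk of sparse cells if injuries are rare. Coding the airway items and writing the missing-value rule takes some work before the next look at the data.

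### The base sample size of 8,800 is not what the named Mann-Whitney test requires (about 7,977); the error is conservative, but 13,112 and 14,943 are built on it

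*Combined protocol and SAP*

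**What the plan says.** All the figures are in the Statistical Analysis section, under Sample size considerations, except the allocation ratio.

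- Assumed proportions with 1, 2, 3 and more than 3 attempts: "0.90, 0.04, 0.03, 0.03 in the direct laryngoscopy group" and "0.92, 0.04, 0.02, 0.02 with videolaryngoscopy".
- Error rates: "with 90% power at the 0.05 significance level". Whether the test is one- or two-sided is not stated.
- Base requirement: "with a Mann-Whitney test we would need a total of 8,800 patients", which the plan describes as "before accounting for interim analyses or within-cluster correlations".
- Correlations of 0.01 within cluster and 0.009 within cluster between periods then raise the total to 13,112.
- Last step: "Further adjustment for interim analyses requires a maximum total of 14,943 patients".
- Allocation, from the Design paragraph of Methods: "Randomization, 1:1 and unstratified".

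The plan gives no formula, software, cluster-period size, rounding rule or safety margin for any step. The paragraph on the internal pilot says that the direct-laryngoscopy distribution and the correlations will be re-assessed at the first interim analysis. The trial will be enlarged if the newly required N is noticeably above the original plan. It does not name the method for that calculation.

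**The concern.** Apart from sidedness, the plan supplies everything needed to reproduce the base figure, and the named test does not return it. That matters for two reasons.

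First, 8,800 is the root of the chain that ends in the maximum enrolment, so a reader who checks the chain fails at the first step and cannot tell which test or outcome the trial was sized on.

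Second, the internal pilot compares a newly computed N with the planned one. If the two come from different methods, part of any difference will reflect the change of method and not the data.

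**Working it through.** **Inputs.** Direct laryngoscopy p = (0.90, 0.04, 0.03, 0.03); videolaryngoscopy q = (0.92, 0.04, 0.02, 0.02); power 90%; alpha 0.05, taken as two-sided; 1:1 allocation. Hence (1.95996 + 1.28155)² = 10.507.

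**Step 1: effect on the Mann-Whitney scale.** Let θ be the probability that a videolaryngoscopy patient needs fewer attempts than a direct-laryngoscopy patient, counting ties as half.

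- Fewer attempts: 0.92×0.10 + 0.04×0.06 + 0.02×0.03 = 0.0950
- Ties: 0.92×0.90 + 0.04×0.04 + 0.02×0.03 + 0.02×0.03 = 0.8308
- θ = 0.0950 + 0.8308/2 = 0.5104

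**Step 2: tie term.** The mean distribution is (0.91, 0.04, 0.025, 0.025). One minus the sum of its cubes is 1 − 0.75367 = 0.24633.

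**Step 3: required total.** N = (z_α/2 + z_β)² × (1 − Σp̄³) / [3(θ − 0.5)²] = 10.507 × 0.24633 / (3 × 0.0104²) = **7,977**, or 7,978 for equal arms. The stated figure is 8,800/7,977 = 1.103 times this.

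**Step 4: power at 8,800.** √(8,800 × 3 × 0.0104² / 0.24633) − 1.96 = 3.405 − 1.960 = 1.445, which gives **92.6%**. Simulation with 200,000 trials gave 90.0% at 7,978 and 92.6% at 8,800.

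**Step 5: do other versions give 8,800?**

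| Calculation | Total N |
|---|---|
| Mann-Whitney, unpooled variance | 7,966 |
| Mann-Whitney, null/alternative variance | 7,972 |
| Mann-Whitney odds | 7,973 |
| Mann-Whitney, one-sided 0.05 | 6,501 |
| Mann-Whitney, no tie correction | 32,382 |
| Mann-Whitney, tie term from control arm only (non-standard) | 8,772 |
| Proportional odds, fitted common odds ratio 1.289 | 7,918 |
| Proportional odds, first-cut odds ratio 1.278 | 8,519 |
| Two proportions, 10% v 8%, uncorrected | 8,601 |
| Two proportions, 10% v 8%, continuity-corrected | 8,800.3 |

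The last two rows follow from n per arm = [1.95996√(2×0.09×0.91) + 1.28155√(0.09 + 0.0736)]² / 0.02² = 4,300.7. The continuity correction is n/4 × [1 + √(1 + 4/(n×0.02))]² = 4,400.14 per arm, or 8,800.3 in total. Rounding each arm up would give 8,802.

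**Step 6: carry-through.**

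- 13,112/8,800 = 1.49 exactly. With 1 + (m − 1)×0.01 − m×0.009 as the design effect, 1.49 corresponds to m = 500 patients per cluster-period, a value the plan does not state.
- 14,943/13,112 = 1.1396. A recomputed inflation for non-binding gamma spending (−4 for efficacy, −1 for futility, four looks) is about 1.134.
- For illustration, 7,977 × 1.49 = 11,886. Multiplying by 1.1396 gives 13,546; by 1.134, 13,478. In round terms these are 11,900 and 13,500.

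**The case against.** The strongest reply is that nothing is lost. The stated aim is 90% power for the assumed difference or a larger one, and 8,800 exceeds what the named test needs. Mann-Whitney is also only a planning device: the primary analysis is a mixed-effects cumulative logit model, with Mann-Whitney as a sensitivity analysis. The assumed distributions are not exactly proportional (cumulative odds ratios 1.28, 1.53 and 1.52), and one proportional-odds version gives 8,519, within about 3.3% of 8,800. So 7,977 is the right number for the label, but not necessarily the requirement of the primary model.

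All of that stands, and it limits the point to a figure that does not match its stated basis. It does not remove the mismatch, because the plan attributes 8,800 to a Mann-Whitney test at 90% power.

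A reader might go further in three ways that the documents do not support.

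- *That 8,800 was computed on first-attempt success as a two-group comparison of proportions.* The agreement is very close, but the plan mentions no such calculation. 8,800 is also a round number, and the control-arm tie variant (8,772) would round to it. That variant is non-standard and simulation contradicts it, so it does not make the figure right, but it is a rival origin.
- *That the internal pilot will conceal up to 10% growth in the required N.* That happens only if the re-estimation uses a different method from the planning. The plan names none, so this is a risk to close and not an established consequence.
- *That the correct maximum is about 13,500, some 1,400 below 14,943.* The multipliers are ratios inferred from the plan's totals. The implied 500 patients per cluster-period also does not sit easily with one-week blocks: 5,000/(52×2) is about 48 per cluster-week, for a design effect of about 1.04. That is a separate question, but it rules out treating the rescaled totals as a target.

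**Conclusion.** The point holds as a mismatch between the named test, the stated power and the stated N. Under a two-sided 0.05 test with 1:1 allocation, the Mann-Whitney requirement is about 7,977 and 8,800 is 10.3% higher, giving about 92.6% power before clustering and interim looks. The sidedness assumption does not explain the gap, since a one-sided test moves further from 8,800. No standard Mann-Whitney version tried reproduces the figure.

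The direction is conservative, so this error does not leave the trial underpowered and gives no reason to doubt its ability to detect the assumed difference. Its importance is that 13,112 and 14,943 inherit it and that the resizing rule refers back to the planned total. The rescaled values of roughly 11,900 and 13,500 only illustrate the size of the carry-through.

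**What to change.** Keep the planned enrolment. In Sample size considerations:

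1. Name the calculation that actually produced 8,800, including its outcome, its sidedness and any continuity correction.
2. State that a two-sided tie-corrected Mann-Whitney test on the assumed distributions needs about 7,978, and has about 92.6% power at 8,800, before clustering and interim looks.

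In the internal pilot paragraph, name one method and use it for both the re-estimated N and the planned N it is compared with, so that a change of method neither masks nor creates a change in the required N.

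The cost is a few sentences of text. No patients are added or removed, and the endpoint, primary model, alpha and trial conduct are unchanged.
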